#### **Planned Secondary Analyses**

Descriptive statistics (means and standard deviations or ns and %s) will be calculated for all secondary outcomes. Secondary outcomes for Aim 1 will be assessed via: 1) daily diary (Homework Adherence during intervention, Headache Frequency, Pain Intensity); 2) monthly survey (Headache Disability Inventory, QIDS-SR (depressive symptoms), MBCT Home Practice inventory, Migraine-Specific Quality of Life, Co-occurring Treatment Tracking, Adverse Events); or administrative data (Survey Completeness, Diary Completeness and Attrition). For secondary outcomes evaluated with daily diary, multi-level mixed effects models will evaluate changes in the outcomes at the day-level across treatment arm (MBCT-T vs. MBCT-V vs. EUC). Repeated measures (day) within person will be taken into account by using person-level random effects. Clusters by group membership will be taken into account using a random effect. Treatment site will be included as a covariate. For secondary outcomes evaluated with monthly surveys, multi-level mixed effects models will evaluate changes in the outcomes at the month-level across treatment arm (MBCT-T vs. MBCT-V vs. EUC). Repeated measures (month) within person will be taken into account by using person-level random effects. Treatment site will be included as a covariate.

#### 9.2 Measures to Minimize Bias

#### 9.2.1 **Enrollment / Masking Procedures**

Subjects will be masked to study hypotheses. They will be informed that they will be assigned to one of three interventions that will last a maximum of 8 weeks and that will provide knowledge to help migraine and depressive symptoms. The facilitators will be unmasked. Data will be entered and coded so that group membership is known only to the project coordinator at NYULH and to research assistants who are coordinating study visits. The investigators will be masked to treatment condition. After study subjects have completed the post-intervention/M2 assessment, the unmasked research assistant will unmask the subjects to study interventions.

#### **Unblinded Personnel:**

NYU Program Coordinator (randomization scheme) Einstein Psychology Assistant (randomization scheme) Wake Forest Research Assistant (randomization scheme) Interventionists at each site YU Research Assistant - Facilitator (Einstein intervention delivery)

Source Documents and Access to Source Data/Documents

Study number: s20-01911 Page 29 Version date: 3/8/2022

Source data is all information, original records of clinical findings, observations, or other activities in a clinical trial necessary for the reconstruction and evaluation of the trial. Source data are contained in source documents. Examples of these original documents, and data records include: hospital records, clinical and office charts, laboratory notes, memoranda, subjects' diaries or evaluation checklists, pharmacy dispensing records, recorded data from automated instruments, copies or transcriptions certified after verification as being accurate and complete, microfiches, photographic negatives, microfilm or magnetic media, x-rays, subject files, and records kept at the pharmacy, at the laboratories, and at medico-technical departments

The study case report form (CRF) is the primary data collection instrument for the study. All data requested on the CRF must be recorded. All missing data must be explained. If a space on the CRF is left blank because the procedure was not done or the question was not asked, write "N/D". If the item is not applicable to the individual case, write "N/A". All entries should be printed legibly in black ink. If any entry error has been made, to correct such an error, draw a single straight line through the incorrect entry and enter the correct data above it. All such changes must be initialed and dated. DO NOT ERASE OR WHITE OUT ERRORS. For clarification of illegible or uncertain entries, print the clarification above the item, then initial and date it.

Access to study records will be limited to IRB-approved members of the study team. The investigator will permit study-related monitoring, audits, and inspections by the IRB/EC, the sponsor, government regulatory bodies, and University compliance and quality assurance groups of all study related documents (e.g. source documents, regulatory documents, data collection instruments, study data etc.). The investigator will ensure the capability for inspections of applicable study-related facilities (e.g. pharmacy, diagnostic laboratory, etc.).

Participation as an investigator in this study implies acceptance of potential inspection by government regulatory authorities and applicable University compliance and quality assurance offices.

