# 7.2 Study Procedures and Evaluations

#### 7.2.1 Study Specific Procedures

#### 7.2.1.1 Further Eligibility Screening

Individuals who meet pre-screening eligibility and who are interested in taking part in this study will be provided with e-Consent materials (hosted on REDCap) and will be scheduled to meet with a Research Assistant via telephone or video to review e-Consent materials, answer questions, and confirm understanding of the study procedures. If still interested, the subject will electronically sign the e-Consent and a pdf copy will be provided to them.

Individuals who meet preliminary eligibility criteria and who consent to participation in this study will stay on the call for further eligibility screening (20-40 minutes). During this eligibility interview, study staff will:

Study number: s20-01911 Page 11 Version date: 3/8/2022

Conduct a structured interview and then review responses with the study neurologist at each site to

ascertain whether the subject meets ICHD-3 criteria for migraine using the American Migraine

• Administer the PHQ-9 to assess depression and suicidality

Prevalence and Prevention Diagnostic Module

Ask additional eligibility questions as outlined in the "Phone Screener" document

Drs. [name], [name], [name], [name], and [name] will provide supervision at their respective sites on depression and migraine inclusion/exclusion criteria and will be available to address any questions regarding these criteria.

Subjects who pass this eligibility assessment will be assigned to an intervention and scheduled for a 30-minute individual orientation session with the intervention facilitator.

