#### 28-Day Baseline Run-In

Participants who meet preliminary criteria and provide informed consent will complete a 28-day baseline run-in to ensure participants meet inclusion/exclusion criteria for migraine diagnosis and the threshold for minimal diary adherence (25/28 days). During the baseline run-in, participants will complete a daily diary including headache symptoms using the REDCap Mobile App or Gene Doe app. If participants do not have a personal device, one will be provided by the research team. The application will prompt a diary entry at a time selected by the participant each evening. If a patient does not submit a daily entry, they will be alerted that the diary entry is still waiting for 12 hours. Participants will not be permitted to record retrospective data to reduce recall bias. Participants who continue to meet inclusion/exclusion criteria after the 28-day baseline run-in will be randomized to receive either 8 sessions of MBCT-T, MBCT-V, or Enhanced Usual Care.

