#### 7.2.1.2 Randomization

Randomization will be stratified by headache days [low-frequency episodic migraine (4-9 days/28 days), high-frequency episodic migraine (10-14 days/28 days)] and gender (male, female). A randomization list will be generated by the study statistician using randomization within random blocks of sizes 3 and 6. Participants will be masked to intervention options and study hypotheses. They will be informed that they will be randomized to one of three interventions that will last a maximum of 8 weeks and that will provide knowledge to help migraine and depressive symptoms. Facilitators will be unmasked. Data will be entered and coded so that group membership is known only to the project coordinator at NYULH and to research assistants who are coordinating study visits. The graduate research assistant who will be coordinating data capture across sites, as well as the investigators, will be masked to treatment condition.

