#### 7.2.1.5 Details of Participant Assessments

Name: Online pre-screener

Type: Other

Time Frame: Pre-screening (online)

Brief Description: The online pre-screener assesses preliminary inclusion and exclusion criteria. See

sections 5.1 and 5.2 as well as the attached document "PRE-SCREENER" for details.

Name: Phone Screener

Type: Other

Time Frame: Screening (verbally, post-e-Consent)

Brief Description: The Phone Screener assesses inclusion and exclusion criteria that are more

nuanced than what is included in the pre-screener and require a member of the study team's training and judgment. Questions will involve assessing depressive symptoms using the PHQ-9. Other questions involve assessing migraine symptoms, many of which will be open-ended, including recent changes to headache symptoms,

medications, and recent hospitalizations.

Name: Migraine Symptoms Checklist

Type: Other

Time Frame: Screening (verbally, post-e-Consent)

Brief Description: The Migraine Symptoms Checklist assesses inclusion criteria. It is a brief structured

interview to guide the formal diagnosis of migraine without aura using the current International Classification of Headache Disorders – 3 criteria. The interview has 15

items to assess migraine without aura.

Name: Patient Health Questionnaire – 9 (PHQ-9)

Type: Other

Time Frame: Screening (verbally, post-e-Consent)

Brief Description: The PHQ-9 assesses inclusion criteria. It is a self-reported measure of depressive

symptom severity and consists of items consistent with criteria for DSM-based diagnosis. PHQ-9 scores range from 0 to 27. Each of the 9 items can be scored from 0 ("not at all") to 3 ("nearly every day"). Cut-points of 5, 10, 15, and 20 represent the

thresholds for mild, moderate, moderately severe, and severe depression,

respectively. The construct validity of the PHQ-9 has been demonstrated in a wide

range of patient populations.

Name: Headache Frequency

Type: Secondary

Time Frame: Headache activity is captured each day during the daily diary from Screening to M3. Brief Description: Headache days/28 days. Each day participants will be asked, "Did you have a

headache today?" with response options of "Yes," and "No." Each day on which a

participant reports "Yes" will be coded as a headache day.

Name: Average Headache Attack Pain Intensity

Type: Secondary

CONFIDENTIAL

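### Section 7.2.1.1 assigns the arm at the phone screen, other sections randomise after the run-in, and the plan does not say how the next allocation is concealed

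*Combined protocol and SAP*

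**What the plan says.** **Timing of assignment.** Section 7.2.1.1, on the phone interview after e-consent: "Subjects who pass this eligibility assessment will be assigned to an intervention and scheduled for a 30-minute individual orientation session with the intervention facilitator". The run-in section that follows: "Participants who continue to meet inclusion/exclusion criteria after the 28-day baseline run-in will be randomized". Section 7.1.4 agrees with the run-in section. It comes after the run-in in the schedule and lists PI confirmation of final eligibility, then randomisation, then a 30-minute orientation for the two MBCT arms only.

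**What the run-in decides.** Section 5.1 requires 4-14 headache days confirmed by prospective diary. Section 5.2 excludes anyone with fewer than 25 of 28 diary days recorded.

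**Sequence.** Section 7.2.1.2: "A randomization list will be generated by the study statistician using randomization within random blocks of sizes 3 and 6". The strata are headache days per 28 days (4-9 or 10-14) and gender. Site is not a stratum. The section does not say how the next allocation is concealed or released.

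**Who knows what.** Section 7.2.1.2 says that "group membership is known only to the project coordinator at NYULH and to research assistants who are coordinating study visits" and that investigators are masked; 9.2.1 repeats this. The list of unblinded personnel tags "NYU Program Coordinator (randomization scheme" and "Einstein Psychology Assistant (randomization scheme) Wake Forest Research Assistant (randomization scheme". Interventionists and a facilitator are separate entries, the facilitator tagged for intervention delivery.

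**Who enrols.** In 7.2.1.1 prospective participants are "scheduled to meet with a Research Assistant via telephone or video to review e-Consent materials", and 7.2.1.5 describes phone-screener items that "require a member of the study team's training and judgment".

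**The concern.** Allocation concealment requires that whoever settles eligibility cannot know the arm that follows. Two features of the text leave this open. First, one operative section puts assignment before the eligibility decisions that the run-in exists to make. Second, the access that goes with the scheme tag is undefined in a plan that describes generation of the list but not its release.

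The stakes are the Aim 2 decision rules. Mean attendance, CSQ-8, retention and HDI/QIDS responder rates feed the choice of Phase III arms, and all plausibly depend on how committed the people in each arm are. MBCT groups start only once 6-8 participants have been assigned (7.1.6), so staff have a practical interest in who enters and when. Masking investigators afterwards does not remove selection at entry.

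**Working it through.** The plan gives no figure to reproduce here. The check is a side-by-side reading plus an illustration of how predictable the sequence is.

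**1. Timing, side by side.**

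| Step | 7.2.1.1 | 7.1.4 and the run-in section |
|---|---|---|
| Phone assessment passed | arm assigned, orientation booked | enters 28-day run-in |
| Diary 25/28 and 4-14 days judged | after assignment | before assignment |
| PI confirms final eligibility | not mentioned | before randomisation (7.1.4) |
| Headache-day stratum | self-report only at that point | diary-confirmed |

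Both cannot be followed. Because 7.1.4 gives the orientation only to the MBCT arms, booking it at the phone screen would itself separate MBCT from EUC. The strata are expressed per 28 days, the length of the run-in, so 7.2.1.1 also sits badly with 7.2.1.2.

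**2. Predictability when block size is known.** With three arms at 1:1:1 and past allocations in the stratum visible, the best guess is the arm with most places left in the block.
- Block of 3: (1/3 + 1/2 + 1)/3 = 61.1% correct; 1/3 = 33.3% of allocations certain.
- Block of 6, by exact enumeration: 56.1% correct; 1.2/6 = 20.0% certain.
- Equal mix, boundaries known: certain (1 + 1.2)/(3 + 6) = 2.2/9 = 24%.

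**3. Predictability when block sizes are unknown.** Assumptions not in the documents: sizes 3 and 6 equally likely, and an even split over the 2 × 2 = 4 strata, so 144/4 = 36 per stratum. A Bayesian guesser updates on the allocations seen and names the most probable next arm.

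| What the person sees | Correct | Certain |
|---|---|---|
| Nothing (chance) | 33% | 0% |
| Past allocations, own site only | about 40% | under 0.1% |
| Past allocations, all three sites | about 57% | about 8% |
| The upcoming list itself | 100% | 100% |

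The own-site row assumes that one third of entries to a stratum come from that site, interleaved at random with the others. The gap between the second and third rows arises because site is not a stratum: each block is shared by three sites, and a person at one site sees only part of it.

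**4. Sensitivity of a decision outcome.** A participant who leaves before Month 2 and cannot be reached is scored 8 on the CSQ-8 (Aim 1B). Relative to a score at the threshold of 24, one such person in an arm of 144/3 = 48 lowers the arm mean by (24 − 8)/48 = 0.33 points. The documents contain nothing from which the size of any actual selection bias could be estimated.

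**The case against.** The strongest reply is that 7.2.1.1 is probably a drafting slip. The order is clear in 7.1.4 and the run-in section, the per-28-day strata fit only that order, and 7.1.4 already has the PI, masked under 7.2.1.2 and 9.2.1, confirm eligibility before randomisation. Diary decisions also leave little discretion: entries are app-prompted, retrospective entry is barred, and the threshold is numeric. All of this stands as mitigation. It does not remove the conflict, because 7.2.1.1 is the text that staff running the interview would follow.

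Three stronger readings are tempting, and the documents do not support them.
- *Site staff hold the future list, so every upcoming allocation is known.* The scheme tag may mean only assignments already made, which is all that 7.2.1.2 and 9.2.1 describe. The text does not settle it.
- *Nothing separates these staff from consent and screening.* Text between 9.2.1 and the list of unblinded personnel was removed from the copy reviewed, so a role separation there cannot be excluded. Sections 7.2.3 and 9.2.1 refer to the unmasked research assistant, which suggests a designated role. Under the post-run-in order, a person taking consent is also at least 28 days ahead of that participant's slot and could not know which slot it will be.
- *Any site assistant can guess the next arm 57% of the time.* That figure needs sight of all three sites.

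**Conclusion.** The point holds in limited form. The conflict over when the arm is assigned is plain on the text and must be reconciled. Following 7.2.1.1 would settle the run-in eligibility criteria with the arm known. The meaning of the scheme tag and the method of concealing the next allocation are not stated in any visible section.

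How far allocation could be anticipated depends on what the tagged staff see: about 40% correct for one site's past allocations, about 57% for all sites', and 100% only if the upcoming list itself is held. The 40% and 57% rest on equal block-size probabilities and 36 per stratum; the 40% also rests on random interleaving of sites. PI confirmation by a masked investigator is a real partial safeguard. A reader might infer that concealment was in fact broken; nothing in the documents shows that. This is a gap in the plan that should be closed.

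**What to change.** 1. In 7.2.1.1, state that subjects who pass the phone assessment enter the 28-day run-in, and that assignment and any orientation follow only after it, in line with 7.1.4.
2. In 7.2.1.2, state that the statistician's list is held centrally and that each allocation is released singly, after the PI has recorded final eligibility.
3. In the list of unblinded personnel, replace the scheme tag with wording that limits these staff to the assignments of participants already randomised. If any of them does need the upcoming list, say so and state that they take no part in consent or screening.

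Taking the block sizes out of the site-facing protocol is optional, as is the choice of release system. REDCap is already used at all three sites for data storage and management, but the documents do not describe a randomisation function in it.

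The cost is a wording amendment and set-up of a central release step. The small downside is that each allocation must be requested rather than read from a list.

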# 10 Quality Assurance and Quality Control

QC procedures will be implemented beginning with the data entry system and data QC checks that will be run on the database will be generated. Any missing data or data anomalies will be communicated to the site(s) for clarification/resolution.

Following written SOPs, the monitors will verify that the clinical trial is conducted and data are generated, documented (recorded), and reported in compliance with the protocol, GCP, and the applicable regulatory requirements (e.g., Good Laboratory Practices (GLP), Good Manufacturing Practices (GMP)).

The investigational site will provide direct access to all trial related sites, source data/documents, and reports for the purpose of monitoring and auditing by the sponsor, and inspection by local and regulatory authorities.

# 11 Ethics/Protection of Human Subjects

### 11.1 Ethical Standard

involved in the clinical trial.

The investigator will ensure that this study is conducted in full conformity with Regulations for the Protection of Human Subjects of Research codified in 45 CFR Part 46.

#### 11.2 Institutional Review Board

The protocol, key information form, consent forms, recruitment materials, and all participant materials will be submitted to the IRB for review and approval. Approval of both the protocol and consent materials must be CONFIDENTIAL

This material is the property of the NYU School of Medicine and NYU Langone Health. Do not disclose or use except as authorized in writing by the study sponsor

Study number: s20-01911 Page 30 Version date: 3/8/2022

obtained before any participant is enrolled. Any amendment to the protocol will require review and approval by the IRB before the changes are implemented to the study. All changes to the consent form will be IRB approved; a determination will be made regarding whether previously consented participants need to be re-

## 11.2.1 Independent (non-NYULH, third party) certified MBCT instructors

If individuals are engaged in human subjects research based on OHRP definition, they are required to obtain their own IRB approval before human subjects research activities are performed.

If individuals are not engaged in human subjects research, PI will ensure there is an executed Business Associate Agreement (BAA) in place before any proposed work is performed by those individuals as contractors. Individuals are considered not engaged in human subjects research if they perform commercial or other services for investigators provided that all of the following conditions also are met:

- the services performed do not merit professional recognition or publication privileges
- the services performed are typically performed by those individuals for non-research purposes
- those individuals do not administer any study intervention being tested or evaluated under the protocol

#### 11.3 Informed Consent Process

consented.

### 11.3.1 Consent and Other Informational Documents Provided to Participants

The following consent materials are submitted with this protocol:

- Study 2 Key Information Sheet
- Study 2 Consent Form
- Study 2 Audio Consent

### 11.3.2 Consent Procedures and Documentation

Informed consent is a process that is initiated prior to the individual's agreeing to participate in the study and continues throughout the individual's study participation. Extensive discussion of risks and possible benefits of participation will be provided to the subjects and their families via telephone or WebEx video-conferencing. Consent forms will be IRB-approved and individuals will be asked to read and review the document. Individuals will have the opportunity to carefully review the e-Consent materials and ask questions prior to signing in REDCap. Individuals should have the opportunity to discuss the study or think about it prior to agreeing to participate. Subjects will sign the e-Consent in REDCap prior to any procedures being done specifically for the study. Subjects may withdraw consent at any time throughout the course of the trial. A copy of the signed informed consent document will be provided via REDCap to the participants for their records. The rights and welfare of the participants will be protected by emphasizing to them that the quality of their medical care will not be adversely affected if they decline to participate in this study.

A copy of the signed informed consent document will be stored in the subject's research record. The consent process, including the name of the individual obtaining consent, will be thoroughly documented in the subject's research record. Any alteration to the standard consent process (e.g. use of a translator, consent from a legally authorized representative, consent document presented orally, etc.) and the justification for such alteration will likewise be documented.

The REDCap e-Consent link will be submitted to the IRB for review in Research Navigator via Modification.

Study number: s20-01911 Page 31 Version date: 3/8/2022

